8.1.6 Evaluation of CDAI

CDAI is a simple linear sum of the following four components:

- Tender joint counts out of 28 joints
- Swollen joint counts out of 28 joints
- Subject global assessment of disease activity (0-10cm)
- Physicians global assessment of disease activity (0-10cm)

8.2 Baseline Measures

For all outcome measures, the baseline value is the last assessment taken prior to first dose of single-blind study medication. In general, this is the assessment taken on study Day 1 before the administration of study medication. For some variables that are also measured during screening, if Day 1 assessments are unavailable then the last assessment prior to Day 1 from screening assessments will be used as baseline value. When there is a missing baseline assessment in joint counts, it will not be imputed. Thus, subjects are excluded from any change from baseline analysis for which they have a missing baseline value.

8.3 Missing Measurements

For listings of efficacy measures or biomarkers, missing values will be represented as missing. For analyses involving efficacy or biomarkers, missing values will not be imputed.

8.4 Missing, Unknown or Partial Dates

The BMS safety guidelines^{2,3,4} for conventions relating to the handling of missing or partial dates and the determination of appropriate default values in such cases (in particular, for concomitant medication dose start dates and end dates and AE onset dates) will be utilized.

8.5 Day Ranges for Analysis of Time Points

Single -blind period

Subjects do not always adhere strictly to the visit schedule timing in the protocol. Therefore, the designation of visits during the single-blind period of the study will be based on the day of evaluation relative to the trial (day of first single-blind study medication = study Day 1) rather than the nominal visit recorded in the CRF. Mutually exclusive relative day windows are defined below to provide derived visits that correspond to the post-baseline time points. If a visit falls outside the pre-specified visit windows, then the data collected at that visit will not be assigned a derived visit but will remain in the derived data sets. Determination of baseline values is addressed in

Section 8.2. The day ranges for assessments during the single-blind treatment period are presented in Table 8.5-1.

Table 8.5-1: Day Ranges for Assessments during Single-Blind Treatment Period

| Visit | Target Day | Assessments |
|------------------|------------|-------------|
| Screening | < 1 | < 1 |
| Day 1 (Baseline) | 1 | 1* |
| Week 4 | 29 | 8 - 43 |
| Week 8 | 57 | 44 - 85 |
| Week 16 | 113 | 86 - 141 |
| Week 24 | 169 | 142 - 211 |

* Note: See [Section 8.3](#) for baseline measures.

For subjects who receive single-blind abatacept and continue into the open-label treatment period, the upper limit of Week 24 window is first dose day of the open-label period. For subjects who receive single-blind adalimumab and continue into the open-label treatment period, the upper limit of this window is the last dose of single-blind study medication + 10 days.

Open-label period

The day ranges for assessments during the open-label period are presented in Table 8.5-2.

Table 8.5-2: Day Ranges for Assessments during Open-label Period

| Visit | Target Day | Assessments |
|---------|------------|----------------|
| Week 28 | 197 | Day 2 OL - 211 |
| Week 32 | 225 | 212 - 253 |
| Week 40 | 281 | 254 - 309 |
| Week 48 | 337 | 310 - 365 |

Efficacy and biomarker assessments performed beyond 42 days after the last dose are excluded.

Lab assessment performed beyond 56 days after the last dose are excluded.

If a subject has more than 1 visit where a measurement is recorded within a window, the measurement closest to the target day will be used. In case of 2 visits being equidistant from the target, the later measurement will be used in analyses.

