6 STUDY PERIODS, TREATMENT REGIMENS AND POPULATIONS FOR ANALYSES

6.1 Study Periods

The following periods are defined for this statistical analysis plan:

- The pre-treatment period covers the time period prior to or on the first dose time of single-blind study medication.
- The single-blind treatment period starts at the time of the first dose of single-blind study medication and lasts until :
 - the time of the last dose of single-blind study medication for concomitant medication summaries
 - 56 days post last dose of single-blind study medication for subjects who do not enter OL. For those subjects who do enter OL, the single-blind treatment period lasts until first day of open-label for abatacept randomized subjects or until 10 days post last dose of single-blind treatment for adalimumab randomized subjects for safety analyses (AE and labs).
 - 21 days post last dose of single-blind study medication for subjects who do not enter OL For those subject who do enter OL, the single-blind treatment period lasts until first day of open-label for abatacept randomized subjects or until 10 days post last dose of single-blind treatment for adalimumab randomized subjects for immunogenicity analyses

Note: To align the cut-off of the single-blind treatment period for abatacept and adalimumab and taking into account that for adalimumab there is a wash-out period of 6 weeks, 10 days is

used to cut the single-blind treatment period for adalimumab. Ten (10) is equal to the expected maximum number of days after last single-blind abatacept dose and prior to first open-label abatacept dose (7 days +/- 3 days).

- The open-label abatacept treatment period starts at the time of the first dose of open-label abatacept treatment and lasts until 56 days post last open-label abatacept dose (AE and labs), except for immunogenicity analyses for which the open-label period goes up to 21 days post last open-label abatacept dose.
- The cumulative abatacept period starts at the time of the first dose of abatacept (single-blind or open-label) and lasts until 56 days post last abatacept dose (single-blind or open-label), except for immunogenicity analyses for which the cumulative abatacept period goes up to 21 days post last abatacept dose.

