7 STATISTICAL ANALYSES

7.1 General Methods

All the analyses, with the exception of the analysis for efficacy responder rate, will be 'as-observed', ie. the available data will be used and there will be no imputation for missing values. For the efficacy responder rate analysis a non-responder imputation will be applied for missing data.

In [APPENDIX 1](#) the list of biomarkers is shown. The different biomarkers are classified into different biomarker categories (category 1 up to 12). The biomarker results (tables and plots) will be provided for each of these biomarker categories separately.

The focus of the exploration will be on Day 169 analysis. However, mean or median changes from baseline (with 95 % CI) over time from day 1 to day 169 of the single-blind period will be displayed for all biomarkers. These plots will be grouped by biomarker category (see [APPENDIX 1](#)).

All Day 337 analyses and analyses over time from day 1 to day 337 (efficacy and biomarkers) will be provided by original randomized treatment and grouped by biomarker category if applicable (see [APPENDIX 1](#)).

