Extent of exposure to single-blind study drug (abatacept and adalimumab) in the as-treated analysis population will be summarized in two ways; first, by the number of study drug doses, summarizing frequency distribution of number of study drug doses by treatment group, and second, by the number of days the subject is known to be on study drug, ignoring any dosing interruptions.

For subjects who are not treated in the open-label period, exposure to single-blind study drug in days is calculated as:

- exposure = (date of last single-blind study medication - date of first single-blind study medication +1) + 56.

The offset of 56 days represents approximately four times the half-life of abatacept in humans.

For subjects who receive single-blind abatacept study drug and enter the open-label period within 56 days of the last dose of single-blind study medication, exposure to single-blind study drug in days is calculated as:

- exposure = (date of first open-label study medication - date of first single-blind study medication).

For subjects who receive single-blind adalimumab study drug, exposure to single-blind study drug in days is calculated as:

- exposure = (date of last single-blind study medication +10 - date of first single-blind study medication).

To align the exposure of adalimumab with the exposure of abatacept and taking into account that for adalimumab there is a wash-out period of 6 weeks, 10 days is used to adjust the exposure for adalimumab. Ten (10) is equal to the expected maximum number of days after last single-blind abatacept dose and prior to the first open-label abatacept dose (7 days +/- 3 days).

Extent of exposure to abatacept (single blind and open-label) during the cumulative abatacept period will be summarized in two ways; first, by the number of abatacept injections, and second, by the number of days the subject is known to be on abatacept, ignoring any dosing interruptions.

$$\text{exposure} = (\text{date of last abatacept dose} - \text{date of first abatacept dose} +1) + 56.$$

The offset of 56 days represents approximately four times the half-life of abatacept in humans.

Abatacept includes single-blind abatacept and open-label abatacept. Exposure will be summarized for cumulative abatacept population and presented for all subjects in this population combined

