7.7.1 Adverse Events

All AEs are coded and grouped into Preferred Terms (PT) by System Organ Class (SOC), using the latest approved version of the Medical Dictionary for Regulatory Activities (MedDRA) at the time of database lock. Listings and summaries will be based on the resulting SOCs and PTs.

All reported AEs during the single-blind treatment period and all reported AEs reported during the cumulative abatacept period will be listed, indicating the subjects id, age, gender, the date of onset, the day of onset relative to the start of treatment, investigator's assessment of severity and relationship to study drug.

In addition, all reported AEs during the washout-out period (beyond 20 days past last single blind dose of adalimumab up to first dose of open-label abatacept) will be in a separate listing. This listing will only include adalimumab patients who are treated with OL abatacept. The threshold of 20 days is chosen for this listing, because AEs up to 20 days past last single-blind dose of adalimumab are included in the AE summaries of the single-blind period. It should be noted that for the single-blind analysis a threshold of 20 days (post-hoc) was used instead of 10 days defined in version 1.0 of SAP.

AEs will be summarized for the single-blind treatment period and the cumulative abatacept period. This period is defined in [Section 6.1](#). These AE summaries will be based on proportions, which represent the number of subjects experiencing the AEs divided by the number of subjects who received at least 1 dose of single-blind study medication for the Week 24 analysis and by the number of subjects treated with abatacept for the cumulative abatacept period analysis.

Any AEs irrespectively of when they occur, but will appear on the above mentioned comprehensive listing.

Summary information (the number and percent of subjects by treatment) will be tabulated for the following AEs:

- all AEs including clinical and laboratory AEs
 - most common AEs (reported in 10% of subjects or more in any treatment group)
 - categorized by severity
- related events
 - most common (reported in 5% of subjects or more in any treatment group)
 - categorized by severity
- serious adverse events (SAEs)
- discontinuations due to SAEs/AEs

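### For adalimumab subjects who enter open label, SAP 8.5 closes the Week 24 window before an on-schedule Week 24 visit can take place

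*SAP*

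**What the plan says.** SAP Section 8.5 assigns visits by actual study day. Week 24 has target Day 169 and a default window of Days 142 to 211. Two exceptions apply to subjects who enter open label:

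- Abatacept: the window ends on the first open-label dose day.
- Adalimumab: "the upper limit of this window is the last dose of single-blind study medication + 10 days".

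If a visit lies outside every window, "then the data collected at that visit will not be assigned a derived visit". The next window, Week 28, opens only on open-label Day 2.

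Section 6.1 explains the figure: "Ten (10) is equal to the expected maximum number of days after last single-blind abatacept dose and prior to first open-label abatacept dose", that is 7 ± 3 days. Section 7.4.1 uses it again for exposure: "10 days is used to adjust the exposure for adalimumab". Section 7.7.1, on adverse events, departs from it: "for the single-blind analysis a threshold of 20 days (post-hoc) was used instead of 10 days defined in version 1.0 of SAP".

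On the use of the data, Section 7.1 says "The focus of the exploration will be on Day 169 analysis". On missing values, Section 7.1 says "For the efficacy responder rate analysis a non-responder imputation will be applied for missing data", while Section 8.3 says "For analyses involving efficacy or biomarkers, missing values will not be imputed".

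**The concern.** The 10 days describes the gap between weekly abatacept doses, but it is applied to a drug given every 14 days. An on-schedule adalimumab subject reaches Day 169 about 14 days after the last dose, when the window is already shut. No other window takes in the visit. No earlier scheduled assessment can replace it, because Week 20 is a phone contact without joint counts, global assessments or HAQ-DI (Protocol Table 5.1-2).

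The loss is confined to one arm and depends on a post-randomization choice, entering open label. As-observed biomarker and continuous efficacy results at Day 169 would compare nearly all abatacept subjects with adalimumab non-continuers and late dosers. For responder rates, under Section 7.1 the lost subjects would count as adalimumab non-responders, which favours abatacept. Under Section 8.3 they would drop out, leaving the same selected subset.

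**Working it through.** **Inputs**

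- Week 24 target Day 169; adalimumab cut-off last dose + 10 (SAP 8.5).
- Switch to abatacept at Week 28 after six weeks of washout (SAP 2.1).
- Adalimumab every 14 days from Day 1 to Week 22, printed as Day 152 (Protocol 4.5.2).
- Dose window ±7 days; last dose at least 7 days before the visit (Protocol 4.5.2.2).
- Visit window ±3 days (Protocol Table 5.1-2, footnote a).

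**1. The SAP's own figure.** 7 + 3 = 10 days. It reproduces, for abatacept.

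**2. Last adalimumab dose.** Day = 7 × week + 1, so Week 22 is Day 155. The 14-day grid 1, 15, …, 155 (12 doses) agrees, and so does the washout: Week 28 is Day 197, and 197 − 42 = 155. Day 152 is not on that grid. The documents must be reconciled; both values are carried below.

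**3. Cut-off against the visit.** Permitted visit days are 169 ± 3 = 166 to 172.

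- From Day 155: 155 + 10 = 165. The target is missed by 4 days and the earliest permitted visit by 1.
- From Day 152: 152 + 10 = 162. The target is missed by 7 days.

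Either way, 0 of 7 permitted days are inside. A Day 169 visit is kept only if the last dose was on Day 159 or later. All seven visit days are kept only with a dose on Day 162.

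**4. Abatacept for comparison.** The last dose is at Week 23, Day 162, and the first open-label dose about Day 169. Dosing follows assessments (Protocol 4.5), so the Week 24 visit is inside the window.

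**5. Allowing for dose timing.** Cross each last-dose day within ±7 days with visit Days 166 to 172, giving 15 × 7 = 105 combinations, and count those with a gap no longer than the limit:

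| Limit | Base Day 155 (doses 148–162) | Base Day 152 (doses 145–159) |
|---|---|---|
| 10 days | 28 (27%) | 10 (10%) |
| 20 days | 95 (90%) | 77 (73%) |
| 24 days | 105 (100%) | 99 (94%) |

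Requiring at least 7 days between dose and actual visit leaves 99 combinations on the Day 155 base; 22 (22%) meet the 10-day limit. The longest gap is 172 − 148 = 24 days on the Day 155 base and 172 − 145 = 27 days on the Day 152 base.

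**6. Illustration of responder bias if Section 7.1 governs.** Spurious difference = p × c × L, where p is the true response rate (equal in both arms), c the fraction of adalimumab subjects entering open label, and L the fraction of those whose Day 169 value is lost. The documents give neither p nor c; I assume p = 0.40 to 0.60 and c = 0.70 to 0.90.

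- L = 1: 0.40 × 0.70 = 0.28 to 0.60 × 0.90 = 0.54.
- L = 0.73 to 0.78 (27% to 22% kept): 0.28 × 0.73 = 0.20 to 0.54 × 0.78 = 0.42.
- L = 0.5: 0.14 to 0.27.

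For scale, SAP Section 5 gives a 95% CI half-width of 17 to 21 points at 40 per arm.

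**The case against.** The strongest reply is the 20-day note in Section 7.7.1. It is in the past tense and speaks of the single-blind analysis, so the sponsor may already have dropped the 10-day limit throughout. Twenty days closes the window on Day 175 from Day 155, or Day 172 from Day 152, and keeps every on-schedule visit. Whether data were actually lost is therefore conditional. But the surrounding sentences concern adverse events, visit windows are not mentioned, and Sections 6.1, 7.4.1 and 8.5 still say 10. Anyone programming from Section 8.5 would use 10. Parts of the SAP are also not visible, so I can say only that the supplied text does not settle the matter.

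Four further points have some force.

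- The ±3-day and ±7-day windows come from the original protocol, and the amended one is not supplied. From Day 155 the cut-off precedes the earliest permitted visit by only one day. The four-day miss of the target, however, follows from the SAP alone.
- Even spacing of doses is an assumption. Protocol 4.5.2.3 treats an extension to ±7 days as exceptional, although 4.5.2.2 gives ±7 as the ordinary window. Fewer late doses would mean fewer visits kept under the 10-day limit.
- Section 8.5 keeps unassigned data in the derived data sets, and no visible text says that such an observation counts as missing for non-responder imputation. The direction of bias rests on that reading. Section 7.1 may also be meant as a specific exception to Section 8.3, but Section 8.3 does not say so.
- The study is exploratory, with no primary or secondary endpoints. That lowers the regulatory stakes but does not justify a one-arm loss in its main randomized comparison.

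**Conclusion.** The concern holds for Section 8.5 as written, on either reading of the last dose day. An adalimumab subject who is dosed on schedule, attends Week 24 within ±3 days and enters open label has no derived Day 169 value, while the corresponding abatacept subject does. Late dosers can be kept: 27% of permitted combinations from Day 155 and 10% from Day 152, if doses are evenly spread. The calendar result assumes that the amended protocol left the ±3 days unchanged. The responder-bias figures are illustrations on assumed rates, not estimates for this trial. If 20 days was in fact applied to the visit windows, the loss largely disappears and what remains is text that contradicts the analysis. This must be corrected, because the stated rule removes on-schedule adalimumab continuers from the Day 169 comparison.

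**What to change.** 1. In Section 8.5, replace the adalimumab continuers' limit with one that contains Days 166 to 172 and ends before the first open-label dose. One form is the earlier of the day before the first open-label dose and the last single-blind dose + 24 days, where 24 = 14-day interval + 7-day dose window + 3-day visit window. On the Day 155 base this covers all 105 combinations, and the latest close, 162 + 24 = Day 186, precedes Day 197. Twenty days would miss 10 of the 105, for example a Day 169 visit after a Day 148 dose. Keep the closest-to-target rule.
2. Reconcile Week 22 with Day 152 in Protocol 4.5.2. If Day 152 is confirmed, the limit must allow for a 27-day gap.
3. State whether the 20-day threshold was applied to efficacy and biomarker windows, and align Sections 6.1, 7.4.1, 7.7.1 and 8.5.
4. State which of Sections 7.1 and 8.3 governs responder rates, and how an observed value without a derived visit is treated.
5. As a query only: check in the amended visit schedule whether switchers have a pre-dose assessment on open-label Day 1, which would be lost because the Week 28 window opens on open-label Day 2.

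The cost is SAP wording and a change to the visit-window program. No new data are needed.

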9 CONTENT OF REPORTS

At the time of the first lock when the last randomized subject completes the 24 week single-blind treatment period, the analyses described in this SAP, with the exceptions of the analyses for the biomarker categories 2, 3 and 5 in [APPENDIX 1](#), will be performed. The results of these analyses will be presented in a standard BMS Clinical Study Report (CSR).
